8.10 Day 30 (±5 days)

Patients who had been discharged from the hospital before Day 25, should return on Day 30 for the following assessments:

- Record the investigator's opinion of etiology of the AP episode
- Record weight
- Perform CECT of the pancreas. May be performed in the 5 days before or after the visit.
- Collect mGCSI-DD worksheets from the patient
- Record concomitant medications
- Record vital signs
- Record the patient's pain using the PNRS
- Record SpO₂ and the FiO₂ (see Section 8.12.6)
- Perform AE/SAE assessment
- Draw blood samples for CBC, differential, platelets, Serum Procalcitonin, and Serum Chemistries - analyze at local lab
- Draw blood sample for Serum IL-6 send to central lab
- Draw a blood sample for PK send to central lab
- Obtain sample for Urine NGAL send to central lab

For patients discharged from the hospital on Days 25-29, the Day 30 assessments may be performed on the Day of discharge.

Patients who are discharged from the hospital on Days 25-29 will not complete the mGCSI-DD after discharge. They will only complete it on the day of discharge.

For patients who remain hospitalized on Day 30, the following additional assessment will be performed:

- Determine if, and when the patient tolerated solid food in the previous 48 hours
- Determine if the patient met the medically indicated discharge criteria in the previous 48 hours (see Section 5.3)

For patients that do not return for Day 30 visit and have not withdrawn consent, the Investigator or designee will continue to contact patient by phone to return for on-site visit up to eight weeks following visit date. Although an out of window visit assessment would be considered a protocol deviation, investigators should attempt to obtain as much as possible all of the Day 30 visit assessments, including the Day 30 CECT.

If patient is not reachable by phone after four weeks following the planned Day 30 visit, the Investigator or designee will send certified letter to last known address to request patient to contact Investigator to either schedule Day 30 visit or at least confirm patient is still alive by telephone. If patient does not respond to certified letter or if patient had withdrawn consent, the Investigator or designee will check public records (e.g., vital records search) to determine if the patient had died prior to the scheduled Day 30 visit or can be assumed alive for the purposes of study follow-up.

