8.11 Discharge Date

The time and date of discharge will be recorded as well as if the patient meets criteria for medically indicated discharge. All patients will be trained to complete the mGCSI-DD and will complete the mGCSI-DD before leaving the hospital. If patients are discharged on Days 25-29, they may complete the Day 30 assessments on the day of discharge. Following discharge, the Investigator or designee should contact patient by telephone once per week to confirm diary completion and patient agrees to return for Day 30 visit.

If a patient is admitted to a hospital following discharge but prior to Day 30 visit, Investigator will report the reason for the hospitalization as per serious adverse event reporting guidelines (See Section 9.2 and Section 9.7). As the patient is still within the study period, investigators or designee should resume collection of study procedures as per Schedule of Events (See Appendix 8). If patient is not admitted to the hospital where the study is being conducted, investigators are asked to record any procedures (i.e., invasive mechanical ventilation) received while patient was admitted during the study period within an unscheduled procedures form in the eCRF.

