10.7 Efficacy Analysis

The efficacy endpoints are the following:

Primary endpoint

Time to solid food tolerance

Secondary endpoints

- Solid food tolerance at 48 hours, 72 hours, and 96 hours after the SFISD and at discharge
- Time to medically indicated discharge
- Length of stay in the hospital
- Length of stay in the ICU for patients admitted to the ICU
- Re-hospitalization for AP by Day 30
- Change in severity of AP by CTSI score from screening to Day 30
- Development of pancreatic necrosis ≥30% and >50%
- The persistence of SIRS ≥48 hours after the SFISD
- Incidence, severity, and duration of organ failure
- Mortality by Day 30
- Change in pain score and opioid use

Exploratory endpoints

- Development of infected pancreatic necrosis
- Development of sepsis
- Hospital procedures for the management of pancreatic necrosis
- Change in GCSI-DD score
- Change in albumin
- Change in ANC/ALC ratio and IL-6 levels
- Change in urine NGAL

Time to solid food tolerance is the number of hours from the date and time of the SFISD for the patient to the first date and time the patient receives a solid meal that is tolerated, which is defined as eating \geq 50% of a low fat, \geq 500-calorie solid meal without an increase in abdominal pain or vomiting in the two hours after completing the meal.

Time to solid food tolerance for patients who could not tolerate solid food during the study will be censored on the latest date and time of food tolerance assessment.

Time-to-event endpoints will be summarized using Kaplan-Meier analyses. The medians and quartiles of time-to-events will be summarized. Time to solid food tolerance will be compared between each treatment groups and the placebo group using the stratified log-rank test as the primary analysis. The tests will be at an alpha level of 0.05 without multiplicity adjustment. The stratification variables will include gender (male vs. female) and disease severity status (higher

risk for organ failure defined by the presence of both a HCT \geq 44% for men, or \geq 40% for women, and a PaO₂/FiO₂ \leq 360 before randomization (Figure 4).

In addition, the hazard ratio (HR) and the 95% CI will be estimated using a Cox proportional-hazard model with treatment group as the independent variable and stratified by the same randomization stratification factors as used for the log-rank test.

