8.6.3 Main Analytical Approach

Time to solid food tolerance through Day 30 visit will be analyzed based on the Generalized Multiple Comparison Modelling (gMCP-Mod) approach described in Session 8.6.1.

Time to solid food tolerance is defined as the number of hours from the date and time of the SFISD for the patient to the first date and time the patient receives a solid meal that is tolerated. If the mealtime was not recorded, the mealtime will be estimated using the middle time of the meal serving interval.

Tolerating a solid meal is defined as eating \geq 50% of a low fat, \geq 500-calorie solid meal without an increase in abdominal pain or vomiting within the two hours of mealtime. In addition, to meet the definition, all subsequent meals during the hospitalization should not show an increase in abdominal pain or vomiting within the two hours of mealtime. If a procedure that could impact food tolerance is performed after a solid meal is initially tolerated that results in subsequent meals not being tolerated, the time of the initial tolerated meal will be considered in the calculation of the time to solid food tolerance. The procedures that impact food tolerance and/or its assessment are defined as (1) a procedure that requires a period of nil by mouth (2) a procedure and/or treatment that causes gastrointestinal dysfunction e.g., cholecystectomy, necrosectomy. The procedures performed after the initial food tolerance will be reviewed before the database lock to identify the procedures that could impact the time to the tolerated solid food. If the subject was not discharged from the hospital during the study and did not tolerate solid food, the time to solid food tolerance will be censored at the latest date and time of the hospital stay.

If a patient is discharged home without tolerating solid food, the daily record of the modified American Neurogastroenterology and Motility Society Gastrointestinal Cardinal Symptom Index Daily Diary (mGCSI-DD) at or after hospital discharge will be used in the calculation of the time to solid food tolerance. The patients who did not tolerate solid food while hospitalized will be considered as tolerating solid food at or after hospital discharge at 8am on the first of three consecutive days where the following 4 criteria are met for the mGCSI-DD:

Protocol CM4620-203 CONFIDENTIAL Page 17 of 31

- none for vomiting
- none or mild for nausea

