- none or mild for not being able to finish a normal sized meal for a healthy person
- none or mild for abdominal pain

If the mGCSI-DD is not available at or after discharge in a patient discharged home without tolerating a solid meal, the time to solid food will be censored at 168 hours.

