8.6.4 Sensitivity Analysis

The sensitivity analysis is to evaluate the assumptions of using the mGCSI-DD in the primary analysis of patients discharged from the hospital without solid food tolerance. Time to solid food tolerance for patients who could not tolerate solid food during the hospital will be censored to 168 hours if the patient is discharged from the hospital during the study and not tolerating solid food. If the subject was not discharged from the hospital during the study and did not tolerate solid food, the time to solid food tolerance will be censored at the latest date and time of the hospital stay.

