8.7 Secondary Endpoint Analyses

8.7.1 Percentage of Patients who Tolerated Solid Food at 48, 72, and 96 Hours from the SFISD and at Discharge

Solid food tolerance will be calculated using the main analytical approach as described in Section 8.6.3.

If the time to first solid food tolerance \leq 48 hours then solid food tolerance at 48, 72 and 96 hours are all yes.

If the time to first solid food tolerance >48 and \leq 72 hours, then solid food tolerance at 72 and 96 hours are all yes and solid food tolerance at 48 hours is no.

If the time to first solid food tolerance >72 and <96 hours, then solid food tolerance at 96 hours is yes and solid food tolerance at 48 and 72 hours are all no.

Protocol CM4620-203 CONFIDENTIAL Page 18 of 31

If the time to first solid food tolerance > 96 hours or the patient never tolerates the solid food during the study then solid food tolerance at 48, 72, and 96 hours are all no.

If the time to first solid food tolerance ≤time to hospital discharge, solid food tolerance at discharge is yes, otherwise, solid food tolerance at discharge is no. If a patient was not discharged from the hospital before end of study, solid food tolerance at the end of study is no.

If it is unknown if solid food has been tolerated at a specific time point (time to first solid food tolerance is censored before the specific time point), the solid food tolerance will be imputed as no.

The proportion and 95% CI of patients who tolerated solid food at 48, 72, and 96 hours from the SFISD, at discharge, and at the end of the study will be displayed using a Clopper-Pearson interval and will be compared between each Auxora treatment group and placebo group using a Cochran-Mantel-Haenszel test stratified by the eCRF recorded sex (male or female) and the risk for organ failure (higher or lower) based on eCRF data. Prohibited immunosuppressive medications or immunotherapies and treatment discontinuation will be ignored (treatment policy strategy).

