8.7.2 Time to Medically Indicated Discharge

The time to medically indicated discharge is the number of days from the SFISD to the first date of meeting the criteria defining medically indicated discharge:

- the patient tolerates solid food, as defined by the main analytical approach; and
- abdominal pain is controlled or resolved, which will be defined by a reduction in pain, as assessed by the PNRS scale, of ≥50% from the peak level in the first 24 hours and no use of opioids; and
- there is no clinical evidence of an infection requiring continued hospitalization.

In patients who do not meet the criteria for medically indicated discharge when discharged from the hospital, the time to medically indicated discharge will be defined as 8am on the first of three consecutive days where the 4 criteria are met for the mGCSI-DD as defined in 8.6.3. If a patient is discharged not meeting the criteria for medically indicated discharged and does not meet criteria for the mGCSI-DD or has not completed the mGCSI-DD, the time to medically indicated discharge will be censored at 168 hours. If the patient dies while hospitalized, the time to medically indicated discharge will be censored at Day 30.

The time to medically indicated discharge will be summarized using Kaplan-Meier analyses. The medians and quartiles of time-to-events will be summarized for each study group. The time to medically indicated discharge will be compared between each Auxora treatment group and placebo group using stratified log-rank test stratified by sex (male or female) and the risk for organ failure (higher or lower). Prohibited immunosuppressive medications or immunotherapies and treatment discontinuation will be ignored (treatment policy strategy).

Protocol CM4620-203 CONFIDENTIAL Page 19 of 31

The proportion and 95% CI of patients who meet the medical discharge criteria by the 96-hour visit and the date of discharge will be displayed using a Clopper-Pearson interval and will be compared between each Auxora treatment group and placebo group using a Cochran-Mantel-Haenszel test stratified by the eCRF recorded sex (male or female) and the risk for organ failure (higher or lower) based on eCRF data. Prohibited immunosuppressive medications or immunotherapies and treatment discontinuation will be ignored (treatment policy strategy).

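### Patients who leave hospital without tolerating solid food are censored at a flat 168 hours or can be given an event before they left, and the primary endpoint states no strategy for death.

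*SAP*

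**What the plan says.** **Censoring time.** Protocol 10.7 says that the time for a patient who never tolerates solid food "will be censored on the latest date and time of food tolerance assessment". SAP 8.6.3 instead sends patients discharged without tolerance to the symptom diary (mGCSI-DD). If no diary is available, "the time to solid food will be censored at 168 hours". In the sensitivity analysis (SAP 8.6.4) the time "will be censored to 168 hours if the patient is discharged from the hospital during the study and not tolerating solid food", diary or not. In both sections, a patient never discharged and never tolerating is censored at the end of the hospital stay. SAP Section 13 lists one departure from the protocol, the ICU-stay analysis.

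**Diaries that do not qualify.** For medically indicated discharge, SAP 8.7.2 says that if the patient "does not meet criteria for the mGCSI-DD or has not completed the mGCSI-DD, the time to medically indicated discharge will be censored at 168 hours". SAP 8.6.3 has no rule for a completed diary that never meets the criteria. Protocol 8.10 adds: "Patients who are discharged from the hospital on Days 25-29 will not complete the mGCSI-DD after discharge".

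**Dating the event.** With a qualifying diary the patient is "considered as tolerating solid food at or after hospital discharge at 8am on the first of three consecutive days". Protocol 8.11 says: "All patients will be trained to complete the mGCSI-DD and will complete the mGCSI-DD before leaving the hospital". SAP 8.7.1 says: "If the time to first solid food tolerance ≤time to hospital discharge, solid food tolerance at discharge is yes".

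**Death.** SAP 8.6.2 lists death among three intercurrent events and attaches no strategy to any of them. SAP 8.7.2 carries in-hospital deaths to Day 30, and 8.7.3 names a composite and a while-alive strategy.

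**The concern.** A censoring time should be the last moment at which the patient was known to be event-free. A fixed 168 h is that moment only by coincidence. It keeps early leavers in the risk set after anyone could see them, and it removes long-stay failures from the risk set while they were still under observation.

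If leaving without a diary is more common in one arm, the first error tilts the hazard ratio and with it the error rate of the proof-of-concept test. The second error shrinks a real difference in the discharge endpoint. The sensitivity analysis in 8.6.4 cannot expose either, because it applies the same 168 h to more patients.

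The 8 am rule can make a patient who left without tolerating food count as tolerating at discharge.

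**Working it through.** **1. From the text alone.**
- Leaves at 60 h, no diary: 168 − 60 = 108 event-free hours credited but not observed.
- Leaves at 240 h, no diary: 240 − 168 = 72 observed hours discarded.
- Later discharges: by SAP 8.1.4.2, Day D falls about (D − 1) × 24 h after the first infusion starts, to within a day. Day 20 = 456 h, Day 25 = 576 h, Day 29 = 672 h. Less 168, these lose 288, 408 and 504 h.
- Discharge on Days 25 to 29: no diary is kept after discharge, so three consecutive qualifying days cannot occur. Sections 8.6.4 and 8.7.2 place these patients at 168 h. Section 8.6.3 has no rule, because a discharge-day diary exists but cannot qualify. A patient still in hospital at Day 30 keeps the full stay in 8.6.3 and 8.6.4.
- 8 am rule: take a discharge at 14:00 with the discharge-day diary as the first of three qualifying days. The event is dated 6 h before the patient left, so 8.7.1 scores tolerance at discharge as yes. The proportion in 8.7.2 meeting the criteria by the date of discharge has the same flaw.
- Death: the only rule in 8.6.3 that fits an in-hospital death before tolerance is censoring at the end of the stay. Section 8.7.2 uses Day 30. A death after discharge without tolerance and without a diary would be censored at 168 h, even if it came earlier.

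**2. Check on the simulation.** The plan gives no figure for these rules. Its nearest is 86% log-rank power for medians of 72 and 144 h with 54 per arm. For exponential times followed to 720 h, events = 54 × [(1 − 2^(−720/72)) + (1 − 2^(−720/144))] = 106.3, and power = Φ(ln 2 × √(106.3/4) − 1.96) = 94.7%. A simulation with nobody leaving also gives 94.7%. By the same formula, 86% corresponds to 168 to 192 h of follow-up (84.3 to 86.5%). The plan does not state the follow-up, so its figure is not disputed.

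**3. Primary endpoint, no true effect.** Inputs: four arms of 54; exponential times; placebo median 100 h (supportive care alone, Protocol 1.5.2), with 72 to 144 h as a range; horizon 720 h; unstratified Cox model; 3,000 trials per scenario. Leaving rates are assumptions. Departure is uniform over 24 to 120 h, and only patients not yet tolerating are censored. A hazard ratio (HR) above 1 means faster tolerance on Auxora.

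The test is the maximum of c′β/√(c′Vc) over the two contrasts in SAP 8.6.1, as listed. With equal arms and a shared placebo, V is proportional to I + J (J all ones). The correlation of the two statistics is 1.231/√(3.975 × 1.250) = 0.55, which gives a one-sided 15% critical value of 1.337.

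| Leaving without a diary, placebo vs each Auxora arm | HR, 168 h | Rejects, 168 h |
|---|---|---|
| 20% vs 5% (12% vs 3% actually censored) | 1.07 (1.06–1.08) | 24% (22–27%) |
| 10% vs 2.5% | 1.04 | 20% |
| 5% vs 20% | 0.94 (0.93–0.94) | 8–10% |
| Balanced | 1.00 | 15% |

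In the 20% versus 5% case, censoring at departure gives HR 0.99 to 1.00 and 15 to 16% rejection.

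**4. Primary endpoint, true HR 2 (placebo median 144 h, two-sided 5%, one dose versus placebo).** With 20% Auxora versus 5% placebo leaving, 168 h gives HR 1.87 and 84% power; departure gives 2.03 and 93%. With 20% in both arms the figures are 1.98 and 89% against 2.02 and 91%.

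**5. Discharge endpoint.** Assume 25% placebo versus 10% Auxora keep a diary but never meet the criteria, with equal speed otherwise. Censoring at 168 h gives HR 1.22 (1.15–1.28) and 14% power (9–21%). Following to Day 30 gives HR 1.49 (1.46–1.50) and 46% (41–47%). Rough check: events ≈ 54 × 0.75 + 54 × 0.90 = 89.1, so power ≈ Φ(ln 1.49 × √(89.1/4) − 1.96) = 47%, and with ln 1.22 it is 15%.

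**6. Deaths.** For deaths at 48 to 480 h and equal speed in survivors, 8% Auxora versus 2% placebo gives HR 0.90 if censored at death and 0.83 if carried to Day 30. At 5% versus 2% the values are 0.94 and 0.90.

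**The case against.** **The affected group is narrow.** In the main analysis 168 h applies only to patients who leave without tolerance and have no diary. The protocol recommends discharge only once food is tolerated, has a diary completed before leaving, and asks sites to telephone weekly. This stands. It limits the size of the bias but supplies none of the missing rules.

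**The 20% versus 5% case is chosen, and its window includes departures before the third dose.** Also fair. With departures limited to 52 to 120 h, HR is 1.05 and rejection 20 to 22%. At 10% versus 5% leaving over the original window, they are about 1.01 to 1.02 and 18%. Dose selection also rests on the totality of efficacy and safety.

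**Discarded hours are not bias.** Correct for the primary hazard ratio: discharge at 168 to 336 h gives HR 1.96 to 2.03 against a true 2. It does not hold for the discharge endpoint, where patients seen to fail are the signal.

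**Censoring at departure may itself be informative.** This is the strongest objection. If no-diary leavers are true failures (25% versus 10%), HR is 1.10 at departure, 1.22 at 168 h and 1.49 at Day 30. Day 30 cannot simply replace departure, however: with non-informative leaving of 20% versus 5% and no true effect it gives 1.28. Both analyses are needed, and 168 h estimates neither quantity.

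**The 8 am wording can be read as barring an earlier event, and death is handled by implication.** Both are possible readings. A programmer should not have to choose between them after database lock.

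**Conclusion.** The concern holds and should be fixed. The flat 168 h, the missing rule for non-qualifying diaries, the conflict over patients discharged on Days 25 to 29, the 8 am dating, the unstated death strategy and the unlisted departure from the protocol all follow from the text without any assumption.

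The size does rest on assumptions, because the documents do not give the share of patients affected. For the primary endpoint the distortion is modest: none on average if leaving is balanced under no effect, and up to HR 1.07 and 24% rejection at a nominal 15% in the most unequal case examined. It reverses with the imbalance. The discharge endpoint loses more: power falls from 46% to 14% if 25% versus 10% never qualify. Backdating under the 8 am rule is less than a day, and how many patients it touches cannot be estimated.

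**What to change.** 1. In SAP 8.6.3, 8.6.4 and 8.7.2, replace 168 h by the patient's own last observation. With no diary, use the last in-hospital food-tolerance assessment, as in the protocol. With a diary that does not qualify, use the last diary day, capped at Day 30; for discharge on Days 25 to 29 that is the day of discharge.
2. Date a diary-based event no earlier than the time of discharge.
3. Derive tolerance at discharge (8.7.1) and discharge criteria met by the date of discharge (8.7.2) from the in-hospital record only.
4. Add one sensitivity analysis that keeps all patients without tolerance, including deaths, at risk to Day 30. Report it beside the main analysis, not in place of it.
5. State the strategy for death in the primary estimand and reconcile it with 8.7.2.
6. List the change of censoring rule in SAP Section 13.

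The cost is SAP wording and programming before unblinding, with no new data. The downside is that some early leavers are censored sooner than now, under an assumption of non-informative leaving; item 4 is there to test that assumption.
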